8.2.1.4 Adverse Events by Preferred Terms (AEs/ADRs/SAEs)

All AEs recorded in CRFs will be classified into the system organ class (SOC) and the terms of AE will be coded according to the classification of AEs in 'WHO-ART'. All AEs, except for 'Unlikely', will be considered as AE whose causal relationship to study drug cannot be excluded (hereinafter "Adverse Drug Reaction (ADR)").

- The number and percentage of AE will be presented overall and by preferred term. This will be repeated by:
 - severity
 - action
 - other action
 - seriousness
 - outcome
 - causality of adverse event to the study drug
 - other causality of adverse event to the study drug
- The number of subjects and the number of unexpected AE/ADR, Serious AE (SAE)/Serious ADR (SADR), unexpected SAE/SADR, AE/ADR will be calculated according to the preferred terms. Also, the proportion of subjects to whom AE occurred will be estimated.
- The subjects with Serious AE, unexpected AE, unexpected serious AE, AE of Geriatric, pregnant, breast-feeding, renal disorder, hepatic disorder and long term subjects will be listed for safety analyses sets.
- For subjects excluded from safety analysis set*, the number of subjects and the number of unexpected AE/ADR, Serious AE(SAE)/Serious ADR (SADR), unexpected SAE/SADR, AE/ADR will be calculated according to the preferred terms. Also, the proportion of subjects to whom AE occurred will be estimated.

* Subjects who enrolled for duplication or Subjects who have not taken PRISTIQ® or Subjects for whom adverse event status could not be established (Adverse Events status is unknown or missing in the CRF) will be excluded from this analysis.

Note: Unexpected AEs/ADRs will be classified by medical review and with reference to the local product document. Terms already included in the local product document are classified as 'expected'. All other terms that are not included in the local product document will be classified as 'unexpected'. These can't be classified without the local product document.

- For subjects excluded from safety analysis set, Serious AE, unexpected AE, unexpected serious AE will be listed for subjects excluded from safety analysis set.

- In re-examination report, SAE/SADR and unexpected AE/unexpected ADR in accordance with PT will be presented respectively according to the frequency categories of adverse events in the approved local label.

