7.3.4. Dosage and administration

The use and dosage recommendations for PRISTIQ® should take place on the basis of the approved local product document. If subjects have been administered PRISTIQ® off label, they should be excluded from the safety analysis set and analyzed separately.

Refer to the most updated local product document for the detailed information on prescription.

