5.1 SAFETY ANALYSIS SET

Subject who have been administered PRISTIQ® at least once and completed follow up will be included in the safety analysis set.

The following exclusions from the Safety Analysis Set are to ensure that the subjects who are not providing data to the analyses but have some record of treatment do not over-inflate the denominator for the analyses.

The following cases are excluded from the safety analysis set:

- Subjects who were enrolled in the study prior to the site initiating contract date

- Follow-up failure: Subjects for whom adverse event status (Adverse Events status is unknown or missing in the CRF) could not be established
- Subjects who violated inclusion/exclusion criteria (see section 2.1)
- Subjects who did not follow dosage and administration indicated in the local product document

To exclude subjects who have ever taken more than 200mg/day

Statistical analysis on safety parameters will be performed on the safety analysis set.

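### The SAP summarises excluded subjects as one group, so no planned output shows adverse events for the off-label subjects whom Protocol 7.3.4 says to analyse separately

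*SAP*

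**What the plan says.** Protocol 7.3.4 states: "If subjects have been administered PRISTIQ® off label, they should be excluded from the safety analysis set and analyzed separately".

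SAP 5.1 carries out the removal. It lists four reasons for exclusion from the safety analysis set:
- enrolment before the contract: "Subjects who were enrolled in the study prior to the site initiating contract date"
- follow-up failure, meaning that adverse event status could not be established
- violation of an inclusion or exclusion criterion
- departure from labelled dosing: "Subjects who did not follow dosage and administration indicated in the local product document". Directly beneath stands the line "To exclude subjects who have ever taken more than 200mg/day".

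SAP 8.2.1.4 then plans two outputs for those removed. The first is a summary by preferred term: "For subjects excluded from safety analysis set*, the number of subjects and the number of unexpected AE/ADR, Serious AE(SAE)/Serious ADR (SADR), unexpected SAE/SADR", continuing to all AEs and ADRs and to the proportion of subjects with an AE. A footnote takes out duplicate enrolments, subjects who never took the drug, and subjects whose AE status is unknown. The second is a listing of serious, unexpected and unexpected serious AEs. Neither is divided by reason for exclusion. SAP Section 5 adds that excluded subjects will be accounted for in the study report and that their adverse events will be described.

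**The concern.** Off-label subjects are kept out of the headline AE incidence (SAP 8.2.1.2) and out of the tables by baseline characteristic (8.2.1.3). The excluded-subject outputs are thus the only planned place where their safety experience appears. There they are mixed with subjects removed for other reasons, one of which, the contract date, is purely administrative and has nothing to do with how the drug was used.

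An assessor who asks how many off-label subjects there were, and how many had an adverse event, could not answer from the planned tables. Expected, non-serious events fall outside the listing and would be tabulated only inside the pooled summary. The protocol's own AE definition (7.4.10.1) names off-label use among the possible sources of signs and symptoms, so the question is a natural one for this surveillance.

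**Working it through.** The plan states no figure to reproduce. The check is which outputs are specified and who is in them.

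**1. Who reaches the excluded-subject summary.** The four reasons in SAP 5.1, set against the footnote in 8.2.1.4:

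| Reason in SAP 5.1 | Dropped by the footnote? |
|---|---|
| Enrolled before site contract | No |
| AE status unknown | Yes |
| Inclusion/exclusion violation | No, if treated |
| Departure from labelled dosing | No |

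4 − 1 = 3 reasons remain, under one denominator.

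**2. Outputs that isolate off-label subjects.** Going through SAP Sections 5, 8.2.1, 8.2.2 and 8.2.3: none. Two AE outputs contain these subjects (the pooled summary and the pooled listing), and neither specifies a field for the reason. The effectiveness set is a subset of the safety set (SAP 5.2), so nothing appears there either.

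**3. What separate analysis means elsewhere in the protocol.** Protocol 7.3.3.1 asks for it for long-term users, and Protocol 7.7 for elderly, hepatic, renal and pregnancy groups. Each of these has its own category in the SAP 8.2.1.3 tables and its own AE listing in 8.2.1.4. Long-term users also have their own effectiveness set (SAP 5.3). Off-label subjects are the only group with this instruction and no output of their own.

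**4. Whether the group is defined.** There are three descriptions: off-label use (Protocol 7.3.4), not following the labelled dosage and administration (the SAP 5.1 bullet), and ever exceeding a stated daily dose (the line beneath it). The third reads as the working rule for the second. Both concern dosing, whereas off-label use can also concern the indication or a contraindication. Protocol Section 5 gives the Korean approval as MDD, and Protocol 7.3.1 and 7.3.2 make MDD and the absence of labelled contraindications eligibility criteria. A subject treated for another indication would therefore be removed as an eligibility violator and could also be off-label. Exclusion reason and off-label status overlap without being the same thing.

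**5. What pooling does to a proportion.** If n of N summarised subjects are off-label, with AE proportion p, and the others have proportion q, the pooled proportion is [n·p + (N − n)·q]/N. Its distance from q is (n/N)·(p − q). The visible share of any difference is n/N, which can lie anywhere from near 0 to near 1. The documents give none of n, N, p or q, so no size can be stated.

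**The case against.** The strongest reply is that Protocol 7.3.4 can be read as asking only for analysis apart from the safety set: "they should be excluded from the safety analysis set and analyzed separately". The SAP does that. The protocol asks for no particular table, column or interval. Protocol 7.7 also allows the SAP to modify protocol plans. The events are not lost: they are tabulated, the serious and unexpected ones are listed, and SAP Section 5 promises a description. The SAP is silent, rather than contrary, on whether the listing or description will show the reason for exclusion.

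Much of this stands. A reader might infer that off-label events go unreported, or that the SAP plainly breaches the protocol. The documents support neither. The parallel in step 3 makes the stricter reading of separate analysis the more natural one, but does not make it the only one. The permission to modify answers less, since the SAP does not say that it is changing this analysis.

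It is also fair to object that the groups are not cleanly distinct. Some eligibility violators may themselves be off-label users, and only pre-contract enrolment is clearly unrelated to drug use. This weakens any claim that off-label experience is swamped by unrelated subjects. It also means that a split by exclusion reason alone would not collect every off-label subject.

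**Conclusion.** The point holds in limited form. With the plan followed as written, an off-label AE count, denominator or proportion cannot be read from any specified output, although the protocol singles these subjects out for separate analysis. In countable terms, three exclusion reasons share one summary and no output is specific to off-label subjects.

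A reader might go further and suppose that pooling hides a material excess of events in off-label users. The documents do not support that. They give no counts or rates by exclusion reason, and if most summarised subjects were off-label the blurring would be slight. The primary safety results are unaffected, because these subjects are outside the safety set in any case. This is an inexpensive improvement to a descriptive surveillance report. The conclusion rests on the wording of SAP 8.2.1.4 alone; table shells that already show the reason for exclusion would resolve it.

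**What to change.** In SAP 8.2.1.4:
- Present the excluded-subject AE/ADR/SAE summary by reason for exclusion.
- Show the off-label group with its own n, number of subjects with an AE, and proportion. A 95% confidence interval is optional; Protocol 7.3.4 does not ask for one.
- Add the reason for exclusion to the excluded-subject listing.
- Flag off-label status across all exclusion reasons, so that an eligibility violator who is also off-label is counted in that group, and state how subjects with more than one reason are shown.

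Reconcile the description of the group in Protocol 7.3.4 with the dosing bullet in SAP 5.1 and the daily-dose line beneath it, by reference to the local product document. Which description is right cannot be judged from these documents.

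The cost is SAP wording, a few columns and some derivation. Reason for exclusion is not a listed CRF item, but it can be derived: SAP 5.1 must already be applied subject by subject, and the CRF holds dosing, diagnosis, eligibility and the privacy-statement date (Protocol 7.4.1, 7.4.2 and 7.4.5). No new data are collected. The downside is that the off-label group may be small and its estimate imprecise, so it should be read descriptively.

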8.2.2 Effectiveness Analyses

Statistical analysis on effectiveness parameter after 8 weeks treatment of PRISTIQ® will be done on effectiveness analysis set.

For collected data separately,

- The overall improvement rate (the proportion of patients considered “Improved”) will be estimated with its 95% confidence interval.
- Frequency and percentage of results for Final Effectiveness (‘Improved’, ‘No change’, ‘Worse’) will be summarized.

The improvement rate according to the baseline characteristics listed in section 8.2.1.3 will be analyzed. Chi-square test or Fisher’s exact test will be used for comparing between subcategories of each baseline characteristic

Additionally, the distribution of subjects according to the CGI-I scale (‘1. Very much improved’, ‘2. Much improved’, ‘3. Minimally improved’, ‘4. No change’, ‘5. Minimally worse’, ‘6. Much worse’, ‘7. Very much worse’) at last visit will be summarized.

Following statistical analysis on effectiveness parameter after 6 months(180 days) treatment of PRISTIQ® will be done on long-term effectiveness analysis set.

- Frequency and percentage of results for Final Effectiveness (‘Improved’, ‘No change’, ‘Worse’) will be summarized.
- Distribution of subjects according to the CGI-I scale (‘1. Very much improved’, ‘2. Much improved’, ‘3. Minimally improved’, ‘4. No change’, ‘5. Minimally worse’, ‘6. Much worse’, ‘7. Very much worse’) at last visit will be summarized.

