7.4.9. Effectiveness Evaluation

7.4.9.1. CGI-I scale (Clinical Global Impression – Improvement scale)

Clinical effectiveness will be evaluated after 8 weeks treatment (within 2 weeks of the last administration) using CGI-I scale as follows. In case of long-term use study subject, the result will be also assessed after 6 months treatment of PRISTIQ® (within 2 weeks of the last administration).

- 1. Very much improved

- 2. Much improved
- 3. Minimally improved
- 4. No change
- 5. Minimally worse
- 6. Much worse
- 7. Very much worse

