7.7.2. Effectiveness analysis

Effectiveness endpoints include following variables: CGI-I scale and final effectiveness evaluation result at the date of effectiveness evaluation. Descriptive statistics (cell counts and percents) will be used to summarize this variable within the effectiveness analysis set population; the CGI-I scale and final effectiveness evaluation will also be summarized within subgroups of the effectiveness analysis set formed by demographic and other baseline factors such as sex, age and diagnosis date of MDD, etc. Comparisons across subgroups may be conducted using chi-squared tests at the 0.05 level of significance.

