1 AMENDMENTS FROM PREVIOUS VERSION(S)

Version	Date of Revision	Reason for change	Author name
Version 1.0	11-MAY-2016	1st Version	PPD
Version 2.0	10-JUL-2016	
 1) Deletion duplicated exclusion criteria in Safety Analysis Set 
 • The contents of “Subjects who didn’t receive PRISTIQ®” are included in “Subjects who violated inclusion/exclusion criteria) item 2) Addition the exclusion criteria in Long-term Effectiveness Analysis Set 
 • Addition “Subjects whose each drug-free period is greater than 14 days” item 3) Modification for analysis method and category 
 • Pregnancy • Breast-feeding • Severity of disease • Mean daily dose of PRISTIQ® 4) Modification of calculation method 
 • “Total administration period of PRISTIQ®” 5) Addition the analysis 
 • Other Analyses (Blood Pressure) 	PPD
Version 3.0	15-NOV-2018	
 1) Modification of calculation of Total administration period of PRISTIQ® according to analysis set 2) Clarification the definition of subjects excluded from safety analysis set 3) Addition items of Basic Results Tables 	PPD
Version 4.0	08-NOV-2019	
 1) Exclusion of subjects who are assessed on the final effectiveness evaluation before 8 weeks treatment with PRISTIQ® from the Effectiveness Analysis Set (Section 5.2) 2) Clarification on the derivation of the mean daily dose of PRISTIQ® excluding days of missed doses (Sections 8.2.1.1) 3) Addition of categories for the Total administration period of PRISTIQ®: <12 weeks, ≥12 weeks (Sections 8.2.1.1 and 8.2.1.3) 4) Addition of AE Listings (Section 8.2.1.4) 5) Addition the analysis 	PPD

		
 AE analysis according to the frequency categories of adverse events in the approved local label (Section 8.2.1.4) 
6) Clarification that the effectiveness analyses will be conducted for the periods after 8 weeks and after 6 months of treatment with PRISTIQ® (Section 8.2.2)
	
--	--	---	--

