5.3 LONG-TERM EFFECTIVENESS ANALYSIS SET

Subject who have been administered PRISTIQ® over 6 months out of enrolled patients will be included in the long-term effectiveness analysis set. The long-term effectiveness analysis set is a subset of the effectiveness analysis set.

The following cases are excluded from the long-term effectiveness analysis set:

- Subjects excluded from effectiveness analysis set listed in section 5.2
- Subjects who administrated PRISTIQ® less than 6 months(180 days)
- Subjects whose each drug-free period is more than 14 days
- Subjects who are assessed on the final effectiveness evaluation before 6 months(180 days) treatment of PRISTIQ®

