6.2 EFFECTIVENESS ENDPOINT(S)

- *[Final effectiveness evaluation]*

Final effectiveness will be evaluated at completing the administration of PRISTIQ® or at around 8 weeks treatment if PRISTIQ® has been still administered. In case of long-term use study subject, the result will be assessed after 6 months treatment of PRISTIQ®. Final effectiveness will be evaluated as 'improved', 'no change', 'worse' or 'unevaluable' based on overall patient's clinical response, CGI-I scale and investigator's judgment.

- Improved: In the case of judgment that there is the improvement of symptoms related to MDD.
- No change: In the case that there is no significant change compared to patient's status before PRISTIQ® administration.
- Worse: In the case that symptoms are getting worse compared to patient's status before PRISTIQ® administration.
- Unevaluable: In the case that the medical charts do not have adequate progress notes to make a judgment on clinical response.

- *[CGI-I scale (Clinical Global Impression – Improvement scale)]*

Clinical effectiveness will be evaluated after 8 weeks treatment (within 2 weeks of the last administration) using CGI-I scale as follows. In case of long-term use study subject, the result will be also assessed after 6 months treatment of PRISTIQ® (within 2 weeks of the last administration).

- 1. Very much improved
- 2. Much improved
- 3. Minimally improved
- 4. No change
- 5. Minimally worse
- 6. Much worse
- 7. Very much worse

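### The 8-week CGI-I table in SAP 8.2.2 takes the rating at last visit, which for long-term use study subjects is, read literally, the 6-month rating

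*SAP*

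**What the plan says.** SAP 8.2.2 has two blocks. The first is introduced by "Statistical analysis on effectiveness parameter after 8 weeks treatment of PRISTIQ® will be done on effectiveness analysis set". It covers the improvement rate, the final effectiveness categories and, as an additional item, the seven-category CGI-I distribution. The second covers treatment of 6 months (180 days) in the long-term effectiveness analysis set, and it also contains a CGI-I distribution. Both CGI-I items close with "at last visit will be summarized".

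Protocol 7.4.9.1 sets the rating schedule: "Clinical effectiveness will be evaluated after 8 weeks treatment (within 2 weeks of the last administration) using CGI-I scale as follows". It then adds: "In case of long-term use study subject, the result will be also assessed after 6 months treatment of PRISTIQ". SAP 6.2 repeats this: "the result will be also assessed after 6 months treatment of PRISTIQ".

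On the populations, SAP 5.3 states: "The long-term effectiveness analysis set is a subset of the effectiveness analysis set". SAP 5.2 removes subjects evaluated before 8 weeks of treatment but sets no latest date.

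Two other places bear on timing. Protocol 7.7.2 names the endpoints as "CGI-I scale and final effectiveness evaluation result at the date of effectiveness evaluation". The SAP change log for version 4.0, which is evidence of intent only, says that "effectiveness analyses will be conducted for the periods after 8 weeks and after 6 months of treatment".

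**The concern.** The heading of the first block names one time point and its selection rule names another. For a subject treated for about 8 weeks the two coincide. For a long-term use study subject, who has two scheduled CGI-I ratings, the last visit is the 6-month one. A programmer who follows the rule as written would pick the 6-month rating for both tables.

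Two things are at stake. The table presented as the 8-week result would mix ratings made at about 8 weeks with ratings made at 6 months or later. For subjects in the long-term set, the two CGI-I tables would hold the same records, so comparing them could show nothing about change between week 8 and month 6. Protocol 7.3.3.1 asks for the long-term data to be analysed separately, and that comparison is a natural use of them.

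**Working it through.** The plan states no figure on this point, so there is nothing to reproduce. The check is mainly textual, followed by an illustration of size.

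**Text, side by side**

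1. Rule for the 8-week CGI-I table (SAP 8.2.2, first block): rating at last visit, effectiveness set.
2. Rule for the 6-month CGI-I table (SAP 8.2.2, second block): rating at last visit, long-term set.
3. Ratings per long-term use study subject (protocol 7.4.9.1, SAP 6.2): two, because the 6-month rating is additional to the 8-week one.
4. Membership (SAP 5.3): every subject in the long-term set is also in the effectiveness set, and so in both tables.
5. Tie-breaker: none. No section defines last visit, sets a visit window, or chooses between two ratings in one subject. SAP 5.2 has only a lower date limit. Protocol 7.7.2 refers to the date of effectiveness evaluation, and these subjects have two such dates for CGI-I.

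From 1 to 5, the literal rule selects the 6-month rating in both tables, and every record of the 6-month table also appears in the 8-week table.

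**Size**

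Inputs from the documents: 600 enrolled (protocol 7.2) and at least 60 subjects treated for over 6 months (protocol 7.3.3.1). Assumed: all 60 qualify for the effectiveness set; that set has N = 300 to 600 subjects; a CGI-I category share changes by d = -10 to +20 percentage points between week 8 and month 6 in these subjects.

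Share of 8-week records that are 6-month ratings = 60/N. Shift in the tabulated share = (60/N) × d. As a yardstick, the 95% half-width at an assumed share of 80% is 1.96 × √(0.8 × 0.2/N).

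| N | 60/N | Shift, d = -10 to +20 | Half-width | d at which shift equals half-width |
|---|---|---|---|---|
| 300 | 20% | -2.0 to +4.0 points | 4.5 points | 22.6 points |
| 400 | 15% | -1.5 to +3.0 points | 3.9 points | 26.1 points |
| 500 | 12% | -1.2 to +2.4 points | 3.5 points | 29.2 points |
| 600 | 10% | -1.0 to +2.0 points | 3.2 points | 32.0 points |

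The last column is the half-width divided by 60/N, calculated before rounding. With 60 subjects the shift stays inside sampling error across the assumed range. Sixty is a minimum: with 120 long-term subjects the shares double to 20% to 40%, and the shift at d = +20 becomes 4.0 points (N = 600) to 8.0 points (N = 300), which is outside the half-width. The documents do not say how many there will be.

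**The case against.** The strongest reply is that the last-visit wording should be read within its block. Each CGI-I item stands under a sentence that names its own period. The observation period in protocol 7.1 and 7.3.3 runs to week 8, so the natural last visit of the main study falls there, and long-term use is described as a separate collection. The version 4.0 log names two periods. A reading that yields two distinct tables is more sensible than one that makes the second a repeat of part of the first. As evidence of intent, all of this stands. It does not override the rule as written: the long-term subjects come from the same enrolled patients, their data run past week 8, and the same undefined words select the record in both blocks. The unclear phrase about separately collected data in the first block introduces the final effectiveness items, not the CGI-I item.

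A second reply is that after 8 weeks may mean 8 weeks or later, so that a 6-month rating is not mislabelled. Protocol 7.4.9.2, which places the final evaluation of subjects still on treatment at around 8 weeks, favours a time point. Even on the open-ended reading, the table mixes times and the overlap with the 6-month table remains.

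A reader might also infer more than the documents support:

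- **That the 8-week improvement rate has the same fault.** Protocol 7.4.9.2 and SAP 6.2 place the final rating of long-term use study subjects after 6 months, without the word 'also'. Whether the CRF holds one final record per subject or two cannot be settled from these documents.
- **That the treatment-duration rows of the improvement-rate split show which record was meant.** SAP 8.2.1.1 does cut the administration period at the final evaluation when treatment continues. But the list of rows is taken over from the adverse event section, and its two rows below 8 weeks are already empty under SAP 5.2. This is a separate matter and does not bear on the CGI-I rule.

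**Conclusion.** The point holds as a minor one. Taken literally, SAP 8.2.2 fills the 8-week CGI-I table with the 6-month ratings of long-term use study subjects, and the 6-month table repeats those records. This is a stated rule that misfires, not just missing detail. It does not show that the analysis was, or would be, run this way; the plan's own headings suggest otherwise.

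With the minimum of 60 such subjects and an assumed set of 300 to 600, 10% to 20% of the 8-week records are affected. The direction of any shift is unknown because the documents give no change from week 8 to month 6. Under the assumed changes and 60 subjects the shift stays within the sampling error of the table. SAP section 4 declares hypotheses and decision rules not applicable, and the CGI-I item carries no test. The consequence is therefore a mixed time point and a lost view of change over time. It would be wrong to infer a distorted decision.

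**What to change.** In SAP 8.2.2:

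- First block: replace the last-visit wording with the 8-week evaluation, defined as the first CGI-I at or after 8 weeks of treatment and within a stated upper window that ends before the 6-month evaluation. The upper limit is needed. No visits are mandated, so without it a subject with no rating near week 8 would still bring a 6-month rating into the table.
- Second block: replace it with the 6-month evaluation (180 days or later).
- Report the number of subjects with no CGI-I in the 8-week window, and do not fill the gap with the 6-month rating.
- State that the same choice of record applies to the final effectiveness rating where the CRF holds both an 8-week and a 6-month record.

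The cost is a few wording edits and one record flag. No new CGI-I data are needed, because the 8-week rating is already scheduled. The downside is a slightly smaller denominator in the 8-week CGI-I table.
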